Appendix 1 - Schedule of assessments			
Appendix 2 - CE Certificate			
Appendix 3 - St Mark's Incontinence Score			
Appendix 4 - Quality of Life Questionnaire			

Appendix 5 - Protocol for MAPLe	
References	40

List of abbreviations

AE	Adverse Event
CI	Chief Investigator
CRF	Case Report Form
FI	Faecal Incontinence
MAPLe	Multiple Array Probe Leiden
AUS	Anal Ultra Sound
HRAM	High Resolution Anal Manometry
ARP	Anorectal Physiology
EMG	Electromyography
sEMG	Surface Electromyogrphy
GCP	Good Clinical Practice
IB	Investigator's Brochure
ICF	Informed Consent Form
ISF	Investigator Site File
MDT	Multi-Disciplinary Team
NHS R&D	National Health Service Research & Development
PI	Principal Investigator
PIS	Participant Information Sheet
QA	Quality Assurance
QC	Quality Control
REC	Research Ethics Committee
SAE	Serious Adverse Event
SDV	Source Document Verification
SOP	Standard Operating Procedure
TMG	Trial Management Group
TSC	Trial Steering Committee

1. Trial personnel

See protocol cover page for Chief Investigator and Sponsor contact details.

Statistician

[name]

e-mail: [contact]

[contact]

2. Summary

Objectives:	Primary Objective: To determine the role of MAPLe in the assessment of Faecal Incontinence (FI) in defined patient groups. Secondary Objective: Identify which patient groups benefit from physiological testing with MAPLe and receive targeted treatment
Type of trial:	This is a multi-centre cohort study investigating FI
Trial design and methods:	The study will take place across two trusts with specialist pelvic floor services.
	Participants will be recruited via referrals for anorectal physiology (ARP) with symptoms of FI meeting the inclusion/exclusion criteria.
	Participants will complete incontinence and quality of life questionnaires, undergo routine ARP with high resolution manometry (HRAM) and anal ultrasound (AUS), and additional assessment with MAPLe. Each assessment will be performed in accordance with a standardised protocol.
	ARP results will be discussed at the local MDT, should treatment be offered, the participant will undergo further testing with MAPLe, if no treatment if offered participation is complete.
Trial duration per participant:	12 months
Estimated total trial duration:	18 months
Planned trial sites:	Multi-Site: University College London Hospitals (UCLH)
	Ashford and St Peter's NHS Foundation Trust (ASPH)
Total number of participants planned:	120

Main inclusion/exclusion criteria:	Inclusion: Symptoms of FI, aged over and including 18, capacity to consent, male/female. Exclusion: anal cancer, anal surgery in the last 3 months, acute/painful perianal disease.
Statistical methodology and analysis:	Non-inferiority testing of MAPLe in the assessment of FI will be performed using Bland Altman method. MAPLe will be tested against HRAM and AUS.
	Participants will be grouped according their pathology: Fistula/chronic perianal disease, Obstetric injury <12 months, Obstetric injury >12 months, neuropathic sphincter. Correlation studies and regression analysis to identify which groups benefitted from MAPLe assessment.
	The clinical utilisation of MAPLe will be determined by the outcome of an expert panel.
	Comparative analysis of participant pre and post treatment MAPLe results will identify if targeted treatment has been achieved.

3. Background and Rationale

Burdon of Disease

Faecal incontinence (FI) is defined as the involuntary passage of gas, liquid or solid stool. The symptom is experienced by an estimated 1-10% of the population. FI is associated with a multitude of disease pathologies and prevalent in vulnerable patient groups, the elderly, learning disabilities or severe co-morbidities, and most prevalent in multiparous females. The degree of symptomatic severity is varied and can result in psychological destress and social withdrawal, severely impacting quality of life in up to 22% of suffers(1).

There is significant economic burden associated with FI. Health economic studies have identified US\$4110 as an average annual cost per person, with an increased cost associated with increased symptom severity(2). Further studies estimated a US \$11 billion annual expenditure and a 55% increase in personal cost of health for sufferers(3). Treatment is symptom orientated, further research would improve understanding of the symptom and direct treatment for more effective outcomes.

Anatomy and Physiology of the Pelvic Floor

FI is the result of impairment to the structure or function of the pelvic floor(4). The pelvic floor, levator ani, is a sheet of muscle supporting the weight of the abdominal cavity. It is divided into four muscle groups: pubococcygeus, ilio-coccygeus, coccyges and puborectalis, assisting the maintenance of faecal and urinary continence.

The anal canal is an opening in the levator ani to allow for passage of stool. The rectum, supported by puborectalis, opens into the anal canal. The anal canal is 4cm long and surrounded by two groups of muscles forming the anal sphincter. The involuntary muscles of the internal anal sphincter (IAS), a continuation of the circular muscle of the rectum. The voluntary muscles of the external anal sphincter (EAS), derived from levator ani. The IAS provides 80% of the resting pressure of the anal sphincter(5).

The sphincter responds to local stimulation via the recto-anal reflex arc, stimulation of the internal sphincter to relax upon distension of the rectum, as well as higher neural stimulation via the spinal cord to relax the external sphincter(6). Damage to the structure of the sphincter complex or its nervous supply reduces the anal tone and results in FI of varying degrees: gas, liquid or solid stool.

Pathogenesis and Aetiology of FI

The pathogenesis of FI is associated with the pathological process of the underlying disease and classified by clinical findings: Anal sphincter weakness, anatomical disturbances of the pelvic floor, anorectal inflammation, central nervous system disease, and bowel disturbances. The most common cause of FI in females is anal sphincter weakness following obstetric injury(7) by direct damage to the sphincter or indirect damage to the pudendal nerve.

Due to the complex and multi-factorial pathogenesis(8), FI is commonly classified by the predominant symptom: passive, urge or mixed.

Current Assessment of the Pelvic Floor

FI is initially assessed in primary care to identify and address lifestyle or medical causes. Patients with persistent symptoms are referred to specialist centres for structural and functional assessment of the pelvic floor(9). Structural assessment includes endoscopy, MRI and Anal ultrasound (AUS)(10). Function, including sensitivity and compliance, is assessed by anorectal physiology studies: anorectal manometry, balloon expansion and expulsion, and barostat investigation(11). Following clinical

review, patients are referred for the appropriate investigation. Patients with symptoms of FI undergo thorough assessment of the structure and function of the anal sphincter.

Structural assessment of the anal sphincter is performed using an anal ultrasound (AUS). The AUS probe is placed into the anal canal. The transducer at the tip of the probe emits sound waves at a frequency between 2.5-6MHz, these reflect against the surrounding tissue and received by the transducer. The volume of sound waves reflected is dependent on the density of the tissue surrounding the probe. The differing structural integrities of the IAS and EAS give distinct appearances. The IAS is seen as a hypoechoic band approximately 1-3 mm in thickness. The EAS appears as a hyperechoic band surrounding the IAS with a thickness of 4-10mm. Abnormalities seen within each band such as lucencies or opacities represent pathology(12). Due to its low risk, low cost and high sensitivity, AUS is the imaging modality of choice for assessing the anal sphincter(13).

Functional assessment of the anal canal is undertaken using anorectal manometry. The technique measures the closing pressures of the anal canal. The test is performed using a probe with between 6-12 pressure sensors along its length. The manometry system can either be solid state or water perfused(14).

The probe is placed within the anal canal and pressures within the anal canal are recorded at rest, voluntary contraction and coughing. The pressures are measured in mmHg and represents the cross-sectional pressure of the canal at each level. The individual structures attributing to the pressure are not identified and the results are representation of the pressures of the pelvic floor as a whole.

Studies have been performed to identify a range for normal results of pressures within the anal canal. The results are dependent on gender and parity. Carrington et al undertook a study of 112 asymptomatic participants using high resolution anal manometry (HRAM) and identified a mean resting pressure of 33-110mmHg in females and 33-114 mmHg in males(15). Further studies have found disparity between age groups (16). Therefore, results require close and careful interpretation by the clinician, taking into account patient symptoms.

Treatment

The NHS spends an estimated £100 million on treatment for FI and it is thought patients experience symptoms for 5 years before seeking treatment. If community management of dietary advice, simple anti-diarrhoeal medication and good toileting (17) fail patients are referred to secondary care. Choice of treatment can vary between trusts due to resources and expertise. The treatment options for FI include: medications, biofeedback, rectal irrigation, neuromodulation and other surgical interventions. Patients are referred in a stepwise progressive pattern. This directed by their response to treatment, quantified by FI scores.

Biofeedback is the process of electronically monitoring an autonomic function to acquire voluntary control. Biofeedback treatment for FI has three elements: rectal sensitivity training to improve awareness and response to stool in the rectum, strength training of the pelvic floor using manometric or electromyographic stimulus, or co-ordination training. Biofeedback treatment protocols are varied(18), however 70-80% experience a 50% improvement of symptoms (19). More recent studies have found no significant improvement in symptoms following treatment with biofeedback(20) and biofeedback has been shown to have the same symptom improvement as dietary advice and routine pelvic floor exercises(21).

Rectal irrigation is a treatment for both constipation and FI. The treatment aim is to maintain an empty rectum(22) preventing incontinence episodes(23). Irrigation is performed using a catheter placed in the rectum through which fluid is irrigated resulting in evacuation of the rectum. The treatment has been found to improve symptoms by 44%.

Short title: Assessment of FI with MAPLe

Sponsor code: 119731

Neuromodulation is a second line treatment for FI in patients with persistent symptoms of FI(24). There are two forms of treatment: sacral nerve stimulation (SNS) and percutaneous tibial nerve stimulation (PTNS). The mode of action is unclear, the treatment applies stimulation to the sacral nerves improving anal sphincter function(25). SNS is an implantable neuromodulator. Prior to implantation, patients undergo a trial period by placement of a temporary wire into the 3rd sacral foramen. If a 50% reduction in symptoms is experienced the patient is offered a permanent implantable device. Studies have shown an 83% continue to have improved symptoms at the 3 years(26). PTNS is a non-implantable form of neuromodulation. The technique was initially developed for the treatment of urinary incontinence; however following reports of improved symptoms of FI further research has been undertaken. NICE references 53% of patients have a good outcome following treatment. However, a recent randomized control trial comparing outcomes following treatment with PTNS vs sham stimulation identified no significant clinical benefit following PTNS treatment(27). Currently PTNS is not recommended for the treatment of FI.

Surgery is performed on the anal sphincter when structural defects are present, most commonly following obstetric injury. The two main surgical techniques used are sphincter repair and sphincteroplasty. Sphincter repair occurs directly after child birth, and is commonly performed by the attending obstetric doctors. Sphincteroplasty is performed by specialist pelvic floor surgeons when large deficits are found on AUS.

Following treatment repeat physiological assessment is not performed as studies have found no improvement(28). Patients who continue to be symptomatic are referred for further treatments.

Rationale

FI is a symptom requiring structural and functional assessment of the anal sphincter to direct choice of treatment. Structural assessment using AUS has been proven to be sensitive(12)(29). Functional assessment can result in a disparity between symptom profile and investigation findings(30) as well as an overlap of results between healthy and symptomatic persons(31). This was shown by Lam et al who identified no correlation between ARP and FI scores in a study of 218 patients. These findings were also reflected in a study undertaken by Zutshi et al on 53 symptomatic females(28). The role of investigatory tests is to guide treatment(30) and although these tests can establish a baseline , both HRAM and AUS are poor predictors of treatment outcome(32). This identifies a need for further study into the assessment of FI.

Novel techniques investigating other properties of the anal canal have been developed. These include assessing elasticity of the anal canal and anal acoustic reflectivity. These techniques are in their early stages and studies so far have shown limited clinical utilisation(33).

Electromyography (EMG) is a technique used to assess the innervation and response of a voluntary muscle fibre to a stimulus. Traditionally EMG is performed using a single needle electrode inserted into a muscle. Following stimulus to voluntarily contract, an action potential is generated along a somatic nerve resulting in a synapse at the neuromuscular junction (NMJ), also called innervation zone, and the release of acetylcholine (ACh). ACh acts on voltage gated channels in the sarcolemma causing depolarisation from the resting potential of -60—90 mV to + 75mV (motor unit potential) resulting in contraction of the muscle fibre. The EMG needle electrode detects the depolarization and records the amplitude (mV) and frequency (Hz). This provides information on individual motor unit potentials resulting from the innervation zone but limited information on overall muscular function. EMG of the EAS requires multiple circumferential punctures into the muscle this is both invasive and painful, limiting the investigation to research and specialist cases.

Studies performed at other centers have investigated the use of surface electrodes (sEMG) on probes(34) placed anally to identify abnormalities or abnormal variants in the innervation and propagation of stimulus within the EAS(35). The anal probes have a series of circumferential sensors that identify the origin and direction of propagation of an action potential. The origin correlates to the

location of an NMJ and innervation zone(19). This technique has been used to investigate asymmetric innervation of the anal canal, particularly important in obstetric medicine(36), but has not progressed from research into clinical utilisation.

The MAPLe device is a new medically certified device distributed by Novuqare using the principals of sEMG in the diagnosis and management of pelvic floor complaints (figure 1).

Figure 1 MAPLe device: anal probe, sEMG detector and charging station.

The probe l has 24 surface electrodes positioned in circumferential bands along its length (figure 2), it is placed in the anal canal. Each sensor detects the sEMG activity in mV for the most proximal muscle fibers (figure 3).

Figure 3 MRI of pelvis with anal probe in situ, confirming correct placement for sEMG detection.

The results are analysed by the receiver to provide numerical values. The values are displayed as a target shaped diagram depicting locational functionality (figure 4 & 5), giving a clear representation of precise areas of weakness in the pelvic floor.

Figure 4 The results can be displayed in three views.

Figure 5 Sensors are grouped together according to the muscle they represent.

The results are displayed on a hand held device in both numerical and diagrammatic formats (figure 6).

Figure 6 Results are displayed on screen in greyscale on target or numerical value.

An independent study tested MAPLe on 229 asymptomatic healthy participants. The study confirmed accurate probe placement to ensure sEMG correlated with correct muscular group, and identified a normal range (27). MAPLe is currently used to provide biofeedback for patients with FI by identifying and targeting muscles with reduced sEMG via visual and electrical stimulation.

The role of sEMG in clinical assessment of FI has been limited to research and has not been correlated with current gold standard techniques. This study aims to investigate the sEMG of symptomatic patients using MAPLe. The study will test the non-inferiority of MAPLe against HRAM and AUS in assessing FI. Non-inferiority of a test is defined as the test being no worse than the competitor. The study will aim to identify if particular patient groups have closer correlation

between symptom profiles and FI scores and sEMG results, and whether sEMG improves following treatment. The study will endeavor to identify the clinical utilisation of sEMG in FI.

3.1 Assessment and Management of Risk

The table below summarise the risks and mitigations of all test above standard care that are being performed in a table:

Intervention	Potential risk	Risk Management
Assessment with MAPLe device	The device will be placed anally and record sEMG, not providing stimulation. As the device will be used in the same nature as current assessment devices no additional risk is perceived.	Performed by trained operator.

4. Objectives

Primary: To determine the role of MAPLe in the assessment of FI in defined patient groups.

Secondary: To determine if targeted treatment is achieved following assessment with MAPLe.

5. Trial design

This is cohort study of participants with symptoms of faecal incontinence. It will take place across two hospital trusts, both able to provide specialist pelvic floor services and facilities required to meet the needs of the study and follow up required by the participants. The use of two sites aims to increase the yield and diversity of participants. The sample size for the study is 120 participants.

Following a stringent selection and recruitment process, participants will be invited to a designated ARP session where they will be consented, complete an incontinence and quality of life questionnaire, and undergo ARP assessment. This will comprise of the current gold standard, AUS and HRAM, and additional assessment with MAPLe using a standardised protocol. Through undertaking all three tests participants will act at their own controls. Participant participation will conclude following ARP assessment unless treatment is deemed necessary by their local MDT. These participants will be followed up at 6 months with interval MAPLe assessment and incontinence and quality of life questionnaire.

The results will undergo statistical analysis to determine non-inferiority of MAPLe in assessing FI. For analysis participants will be allocated to the following groups: fistula/chronic perianal conditions, obstetric injury <12 months, obstetric injury >12months, neurogenic. Each group will be analysed using symptoms profile and MAPLe results to identify correlation. Comparison of MAPle results pre and post treatment will determine if targeted treatment has been achieved.

An expert panel of pelvic floor specialists will be formed to determine the additional benefit of MAPLe in a clinical context. The panel will consist of 3-6 specialists within the field. To reduce bias,

each specialist will be provided with literature on the background of MAPLe and how to analyse the results. The panelists will receive up to date guideline on the management of FI. The panel will be provided with cases and ARP results to answer the following questions:

Question 1: What is the additional benefit of MAPLe?

- □ Panelists will be provided with clinical history HRAM and AUS results
 - What is the diagnosis and how will you manage this patient?
- □ MAPLe results provided
 - Has the management changed?
 - How beneficial on scale 1-10 has the addition been?

Question 2: HRAM and AUS vs MAPLe and AUS

- □ Panelists will be provided with a series of paired histories set one with HRAM and AUS results, set two with MAPLe and AUS results
 - What is the diagnosis and treatment?
 - How confident do you feel in your diagnosis and treatment for set two?

Question 3: MAPLe alone

- □ Panelists will be provided with history and MAPLe results
- \Box What is the diagnosis and treatment?
- □ Do you feel enough information is provided by the MAPLe to allow for a management plan?

The outcomes of the expert panel will undergo statistical analysis.

6. Selection of Participants

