11.1 Primary Outcome

They primary outcome is to determine which participant groups benefit from assessment with MAPLe. Benefit will be determined by correct identification of abnormalities in symptomatic participants using MAPLe, correlation between symptom profile and MAPLe results, and the outcome of the expert panel. It will be measured once the end of recruitment is reached.

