11.5 Statistical analysis

11.5.1 Primary outcome analysis

Non-inferiority testing of MAPLe will be performed using Bland-Altman method. Correlation between MAPLe and AUS for location of sphincter abnormality will be identified. Correlation between MAPLe and HRAM for functional abnormalities will be identified.

Participants will be allocated a patient group dependent on the cause of FI:

- □ Fistula/ chronic perianal conditions
- \Box Obstetric injury <12 months
- \Box Obstetric injury > 12 months
- □ Neuropathic

Each group will be analysed using correlation studies and regression analysis to determine which groups benefit from MAPLe assessment.

The clinical benefit of the addition of MAPLe assessment will be determined from the analysis of the results of the expert panel.

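### Expert panel Question 1 cannot record a detrimental effect of adding MAPLe: the rating leans towards benefit and the change item has no direction

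*Combined protocol and SAP*

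**What the plan says.** Section 5 (Trial design) sets up a panel of 3-6 specialists and gives it three questions.

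- **Question 1** tests adding MAPLe. With the clinical history, HRAM and AUS in hand, the panellist is asked "What is the diagnosis and how will you manage this patient". MAPLe results are then supplied, and two items follow: "Has the management changed" and "How beneficial on scale 1-10 has the addition been".
- **Question 2** sets HRAM with AUS against MAPLe with AUS on paired histories. It asks for diagnosis and treatment, and then "How confident do you feel in your diagnosis and treatment for set two".
- **Question 3** gives the history and MAPLe alone and ends with "Do you feel enough information is provided by the MAPLe to allow for a management plan".

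Section 11.1 defines the primary outcome through three components: "Benefit will be determined by correct identification of abnormalities in symptomatic participants using MAPLe", then "correlation between symptom profile and MAPLe results, and the outcome of the expert panel". Section 11.5.1 adds: "The clinical benefit of the addition of MAPLe assessment will be determined from the analysis of the results of the expert panel". None of these sections gives wording for the points of the 1-10 scale, a method for analysing the panel's answers, or a result that would count as benefit or no benefit.

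**The concern.** A diagnostic test can help a decision, leave it alone or mislead it. An instrument meant to judge the clinical value of adding a test should be able to record all three. After MAPLe is shown, Question 1 has a place for the first, an ambiguous place for the second and none for the third.

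The rating asks how beneficial the addition was, so the panellist is asked for a degree of benefit. Someone who found the MAPLe result confusing can do no more than choose a low number, as can someone who found it merely redundant. The change item counts a move to a worse plan exactly as it counts a move to a better one.

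Of the three components in section 11.1, only the panel looks at clinical decisions, and within the panel only Question 1 looks at the same case before and after MAPLe is added to the current tests. Once the panel has sat, the missing information cannot be recovered.

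**Working it through.** The plan gives no figure for the panel analysis, so there is none to reproduce. Its only design figure is the sample size in section 11.3 (4 groups x 30 = 120), which reproduces; this point does not depend on it. The check is to list what each item asked after MAPLe can show.

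**1. The rating.** Input: the 1-10 range in section 5. The minimum is 1 and the midpoint is (1 + 10)/2 = 5.5. No value is given a meaning. A 1 may be read as no benefit or as a little benefit, and 5.5 is not described as neutral. No value is set aside for a detrimental effect, so redundant and misleading readings have no separate places on the scale.

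**2. The change item: can it show no effect?** Yes. The share of cases changed, c, can run from 0% to 100%. If no case changed among n cases, the exact 97.5% upper limit is 1 - 0.025^(1/n):

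- n = 30: 1 - 0.025^(1/30) = 11.6%
- n = 120: 1 - 0.025^(1/120) = 3.0%

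The plan does not say how many cases the panel will see; 30 and 120 are borrowed from section 11.3 for illustration, with one independent answer per case. A finding of little or no influence is therefore available.

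**3. The change item: can it show direction?** No. Let w be the share of changes that were for the worse. The net effect is c(1 - w) - cw = c(1 - 2w). Both c and w are assumed, because the documents give neither.

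| Share changed, c | w = 0 | w = 0.25 | w = 0.50 | w = 0.75 |
|---|---|---|---|---|
| 20% | +20% | +10% | 0% | -10% |
| 40% | +40% | +20% | 0% | -20% |

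For example, 0.4 x (1 - 2 x 0.75) = -0.2. Question 1 would report every entry in a row as the same number.

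**4. Could direction be recovered from other answers?** Question 1 asks for diagnosis and management before MAPLe is shown, but as worded it does not ask for either again afterwards. The starting plan is known and the end plan is not. Question 2 concerns replacing HRAM with MAPLe, and Question 3 concerns MAPLe alone. Neither supplies the plan that a panellist would choose with all three tests.

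**The case against.** A reader might infer that the panel criterion is bound to favour MAPLe. The documents do not support that. Management could be unchanged in every case, and ratings clustered near 1 would be an unfavourable result. With no cut-off set in sections 5, 11.1 or 11.5.1, the criterion is undecided rather than certain to be positive.

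A reader might also treat Question 1 as the primary criterion itself. It is one of three panel questions, and the panel is one of three components. Question 3 can be answered no.

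Nor is the panel without any comparator. Question 2 has one built in, HRAM with AUS, which section 5 calls the current gold standard, although no analysis of it is described. Section 5 also gives panellists background literature and management guidelines with the aim of reducing bias.

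All of this stands, and it limits the point to Question 1 and to harm. It does not fill the gap: none of these features lets a panellist record that adding MAPLe made a decision worse, or lets an analyst see which way a plan moved. It could be said that the final form may carry worded points or space for the new plan. The documents describe neither.

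**Conclusion.** The point holds in a limited form. Question 1 can show that MAPLe had little influence, but it cannot show that the influence was detrimental, and its rating is worded towards benefit. The size of any resulting bias cannot be calculated, because the documents give no expected share of changed plans and no share changed for the worse. Under the assumed 40% changed, one reported figure covers net effects from +40% to -20% as the share for the worse runs from none to three quarters.

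The conclusion assumes that the form will be used as worded in section 5, without further items or worded scale points. It is a fault in one instrument that contributes to the primary outcome and does not invalidate the study. It should be fixed, and this has to happen before the panel sits.

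**What to change.** Make three changes to Question 1:

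1. Replace the 1-10 item with a two-sided scale described in words: -5 confusing or detrimental, 0 no effect, +5 helpful.
2. Have each panellist record diagnosis and plan from one fixed list, before MAPLe is shown and again after. Derive the change from the two records in place of the yes/no item.
3. Report the numbers of positive, zero and negative ratings separately, not only a mean. On the new scale, half the ratings at +5 and half at -5 average 0.5 x 5 + 0.5 x (-5) = 0, the same as a test with no effect in any case.

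The cost is a slightly longer panel form and a fixed list agreed in advance. One limit remains: a self-rated scale misses errors that the panellist does not recognise, and the paired plans show what moved without showing which plan was right.

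It is tempting to settle that by using the 6-month St Mark's score as a reference. This should not be done. Improvement on one treatment without a control does not show that this plan was right or another wrong. Appendix 1 marks the incontinence questionnaire at Day 1 only, whereas section 5 promises it at 6 months and section 11.2 relies on it; those places need reconciling in any case. Waiting for the score would also delay an outcome that section 11.1 places at the end of recruitment.
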